5.4. Vital Signs and Physical Examination Findings

Vital signs (systolic and diastolic blood pressure, pulse, and temperature) values collected immediately before Day 1 of each cycle and change from baseline will be summarized.

Similar analyses will be performed for weight at Day 1 of each treatment cycle.

Post baseline physical examination findings were collected as AEs, and therefore will not be summarized.

5.5. Electrocardiogram (ECG)

Electrocardiograms (ECG) will be performed at Screening, Day 1 of Cycle 3 and Cycle 6, and End-of-Treatment visit. If blood sampling or vital sign measurement is scheduled for the same time point as ECG recording, then the procedures should be performed in the following order: ECG(s), vital signs, blood draw.

The number and percentage of subjects with normal, clinically significant or clinically non-significant abnormal 12-lead ECG results will be summarized at each scheduled visit by NHL subtype.

5.6. Other Safety Parameters

5.6.1. ECOG Performance Score

ECOG performance status, which evaluates the effect of the disease status on the activities of daily living, will be assessed at Screening, Day 1 of Cycle 1, 3, 5, 7, every 12 weeks after Cycle 7 and 16 weeks post PD. Descriptive statistics will be used to summarize ECOG performance status at baseline and post-baseline (including change from baseline) for each NHL subtype.

6. PHARMACOKINETICS/PHARMACODYNAMICS

Unless specified otherwise, descriptive statistics (eg, number of observations, mean, standard deviation, median, and range) will be used to summarize pharmacokinetics and pharmacodynamics data. In addition, coefficient variation and geometric mean will be provided in the pharmacokinetic concentration summary.

6.1. Pharmacokinetics

6.1.1. Sampling Time Points

For all subjects, pharmacokinetic samples to determine serum concentration of daratumumab will be obtained on Day 1 of Cycle 1, 3, 5, 7, 11, 15, and 4 weeks and 8 weeks after last daratumumab dose. On a daratumumab dosing day, blood samples need to be collected before (up to 2 hours but not after the start of infusion) and immediately after (up to 2 hours but not before the end of infusion) daratumumab administration.

6.1.2. Pharmacokinetic Parameters

The pharmacokinetic parameters are defined as:

C_{max} Maximum observed concentration

C_{min} Minimum observed concentration

Pharmacokinetic samples to determine serum concentration of daratumumab will be obtained from all subjects. Pharmacokinetic endpoints include:

- Minimum observed concentration (C_{min})
- Maximum observed concentration (C_{max})

If sufficient data are available, then other pharmacokinetic parameters may be calculated.

6.1.3. Analysis Methods

Pharmacokinetic analyses will be performed on the pharmacokinetic-evaluable population, defined as subjects who have received at least 1 dose of daratumumab and have at least one postinfusion sample.

All serum concentrations below the lowest quantifiable concentration in a sample or missing data will be labelled as such in the concentration data listings. Concentrations below the lowest quantifiable concentration in a sample will be treated as zero in the summary statistics. All subjects and samples excluded from the analysis will be clearly documented in the Clinical Study Report.

Descriptive statistics will be used to summarize daratumumab serum concentrations at each sampling timepoint and pharmacokinetic parameters of daratumumab. C_{min} is defined as the concentration observed immediately before infusion and C_{max} is defined as the concentration observed at the end of infusion, as presented in the summary of serum concentration by sampling time point. Other pharmacokinetic parameters may also be summarized.

If sufficient data are available, then population pharmacokinetic analysis of serum concentration time data of daratumumab may be performed and may include data from other studies. If the population pharmacokinetic analysis is conducted, then details will be given in a population pharmacokinetic analysis plan and the results of the analysis will be presented in a separate report.

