For DLBCL, the null hypothesis is that the ORR is at most 15%, and the alternative hypothesis is that the ORR is at least 30% for all subjects, or at least 40% for those subjects whose CD38 expression level is above a to-be-determined level. These were based on the clinical observation that relapsed DLBCL subjects who are not eligible for HDT/ASCT have a very poor prognosis and no established therapeutic options.

For FL, the null hypothesis is that the ORR is at most 30%, and the alternative hypothesis is that the ORR is at least 50% for all subjects, or at least 60% for those subjects whose CD38 expression level is above a to-be-determined level. These are based on the published ORRs of idelalisib (54%, which was the basis of an accelerated approval in the U.S.) and rituximab monotherapy (49%, Coiffier 2011).

For both DLBCL and FL, 55 subjects may be enrolled. Thirty-five (35) of those must have tumors with 50% or more cells positive for CD38 expression at baseline in order to rule out that any lack of activity is mostly due to low CD38 expression level in the enrolled subjects.

The trial will be carried out in two stages within each NHL subtype, as in a Simon's two-stage design. Each NHL subtype, independent of the other subtypes, may be discontinued after Stage 1 due to futility. To exclude the possibility that an observed low response rate is due to low CD38 expression level at baseline, the trial will enroll sufficient number of subjects with tumors where $\geq 50\%$ of cells are CD38 positive in both stages. The detailed procedure will proceed as follows.

For MCL, Stage 1 will accrue 20 subjects with tumors where $\geq 50\%$ of cells are CD38 positive. If the futility criteria are met (at most 4 responses overall), no further expansion is planned. Otherwise, an additional 80 subjects will be enrolled to Stage 2; at least 50 of these subjects will have tumors where $\geq 50\%$ of cells are CD38 positive. The sample size will provide approximately 85% power to reject the null hypothesis for the overall population with a one-sided significance level of 0.04.

For DLBCL, Stage 1 will accrue 15 subjects with tumors where $\geq 50\%$ of cells are CD38 positive. If the futility criteria are met (at most 3 responses overall), no further expansion is planned. Otherwise, an additional 40 subjects will be enrolled to Stage 2; at least 20 of these

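### Setting below-quantification concentrations to zero makes the planned geometric mean 0, or undefined on the log scale, at any time point with one such value, and the SAP does not reconcile the two rules.

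*SAP*

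**What the plan says.** Two statements in the SAP have to be read together.

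- **Handling of low values (SAP 6.1.3).** "Concentrations below the lowest quantifiable concentration in a sample will be treated as zero in the summary statistics". No statistic is exempted.
- **Statistics to report (SAP 6, introduction).** Beyond the number of observations, mean, SD, median and range, "coefficient variation and geometric mean will be provided in the pharmacokinetic concentration summary".

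The level of the summary and the schedule determine where the two meet.

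- **Level (SAP 6.1.3).** "Descriptive statistics will be used to summarize daratumumab serum concentrations at each sampling timepoint and pharmacokinetic parameters of daratumumab".
- **Schedule (SAP 6.1.1).** Samples "will be obtained on Day 1 of Cycle 1, 3, 5, 7, 11, 15, and 4 weeks and 8 weeks after last daratumumab dose". On dosing days, "blood samples need to be collected before (up to 2 hours but not after the start of infusion) and immediately after" the infusion. The first pre-infusion sample is therefore taken before any study drug. SAP 6.2.1 also lists a Cycle 1 Day 1 predose sample.

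SAP 6.1.3 defines Cmin as the pre-infusion concentration and points to this same by-time-point table for it. SAP 6.1.2 names Cmin as a pharmacokinetic endpoint.

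**The concern.** The geometric mean does not tolerate zeros. The arithmetic mean and median absorb a few of them, but one zero erases the information in all the other values. The zero rule therefore suits some of the listed statistics and not this one, and the SAP applies it to all of them.

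What is at stake is the readability of the concentration table, including the rows that report Cmin. If a programmer meets a zero, the plan leads either to a printed geometric mean of 0 or to a failed logarithm. Any other entry would need a convention that the SAP has not stated. SAP Section 1 adds some weight: if futility criteria are met, this interim SAP becomes the study SAP, so a later plan may not arrive to settle the point.

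**Working it through.** The documents give no figure on this point to reproduce. The check is algebraic, with a numerical illustration.

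**Inputs from the SAP.** The zero rule (6.1.3), the statistics (6, introduction), the time points (6.1.1), and the Stage 1 cohort sizes for scale (1.2): "For MCL, Stage 1 will accrue 20 subjects" and "For DLBCL, Stage 1 will accrue 15 subjects", with FL the same as DLBCL.

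**Assumed inputs, not in the documents.** The quantification limit, the concentration distribution and the rate of below-limit values.

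**1. One value below the limit.** Geometric mean = (x₁ × x₂ × … × xₙ)^(1/n) = exp[(1/n) Σ ln xᵢ]. With one xᵢ = 0 the product is 0, so the geometric mean is 0 for any n and any other values. In the log form, ln(0) is undefined.

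**2. All values below the limit.** The geometric mean is again 0 or undefined. The coefficient of variation is SD/mean = 0/0, which is undefined. This is the expected state at Cycle 1 Day 1 pre-infusion, assuming no earlier daratumumab exposure and no assay background.

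**3. How far the answer depends on the convention.** The illustration uses 20 simulated lognormal values (median 100 arbitrary units, log-SD 0.5), with one replaced by a below-limit value. For a substituted value s, geometric mean = (geometric mean of the other 19)^(19/20) × s^(1/20). With 98.2 for the other 19, s = 0.05 gives 67.2 and s = 1.0 gives 78.0. The n = 15 column was done the same way.

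| Handling of the one low value | n = 20 | n = 15 |
|---|---|---|
| Set to zero (SAP rule) | 0 | 0 |
| Excluded | 98.2 | 104.0 |
| Half the limit, or the limit, substituted (assumed limit 0.1 to 1.0) | 67.2 to 78.0 | 62.5 to 76.3 |

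Before the replacement, the geometric means were 99.7 (n = 20) and 104.9 (n = 15). The replaced value was arbitrary, so the shift from 99.7 to 98.2 does not measure bias. The useful comparison is between rows: exclusion sits above substitution. Under the zero rule the arithmetic mean moves only from 116.4 to 109.6 for n = 20, so the rule is tolerable for that statistic.

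**4. How likely a zero is after the first dose.** If each sample is below the limit with probability q, independently, P(at least one) = 1 − (1 − q)ⁿ.

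| Assumed q | n = 15 | n = 20 |
|---|---|---|
| 1% | 1 − 0.99¹⁵ = 14% | 1 − 0.99²⁰ = 18% |
| 5% | 1 − 0.95¹⁵ = 54% | 1 − 0.95²⁰ = 64% |
| 10% | 1 − 0.90¹⁵ = 79% | 1 − 0.90²⁰ = 88% |

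These figures take every Stage 1 subject as sampled at the time point. Fewer samples would lower them.

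**The case against.** The case for leaving the text alone has four parts.

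- **The rules can be executed.** A reader might infer that the two rules cannot both be carried out. That goes too far. In product form the geometric mean can be computed and equals 0. Only the log form fails. What stands is that the executed result is uninformative.
- **The near-certain case is harmless.** Before the first infusion the concentration should be about zero, so a geometric mean of 0 or a blank misleads nobody. This stands. Elsewhere the problem depends on below-limit rates that the documents do not give, so it is conditional.
- **Silent dropping is not what the plan describes.** A reader might infer that software will discard zeros unnoticed and that reported exposure will be overstated. The documents say nothing of software behaviour. SAP 6.1.3 requires below-limit results to be flagged in the listings and requires the study report to document any excluded samples. An unrecorded exclusion would depart from the plan. These safeguards make the problem visible but do not say what number goes in the table.
- **Little depends on it.** The median and range remain available with zeros present, any population pharmacokinetic model has its own plan, and the futility guideline in SAP 1.1 counts responses. This stands, and it limits the point to a minor one.

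**Conclusion.** The point holds as a minor inconsistency between two stated rules. Followed exactly, the SAP yields a geometric mean of 0 (undefined on the log scale) at any time point with one below-limit value, and an undefined coefficient of variation where all values are below the limit. That part rests on algebra alone.

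The practical size is small at Cycle 1 Day 1 pre-infusion. At later Cmin samples and at the two post-treatment samples it is unknown. There the effect would be a lost or convention-dependent geometric mean, and the probabilities and simulated values above only show scale under assumed inputs. The documents do not support a claim that any reported geometric mean will be wrong at those later time points. The response rate analysis and the futility decision are not touched.

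**What to change.** Amend SAP 6.1.3 in three respects:

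1. Limit the zero rule to the arithmetic mean, SD, median and range.
2. Exempt the geometric mean and state its convention in advance. One option is to use quantifiable values only and print the number below the limit beside the result. This places the geometric mean on a different set from the arithmetic mean and tends upward, so the SAP should say so; the count discloses that tendency but does not remove it.
3. Report the geometric mean and the coefficient of variation as not calculated when no value at the time point is quantifiable.

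A stricter cut-off for suppressing the geometric mean, such as a set proportion below the limit, would be the sponsor's choice. Nothing in the documents points to a particular value.

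The cost is a sentence or two of SAP text and a matching footnote in the table. Sampling, data collection and trial conduct do not change.

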6.2. Immunogenicity

6.2.1. Sampling Time Points

Samples to assess the generation of antibodies to daratumumab (immunogenicity) will be obtained from all treated subjects at Cycle 1 Day 1 predose, Post-Treatment Week 4, and Post-Treatment Week 8. In addition, any time an infusion-related reaction is observed during the study, an unscheduled blood sample should be drawn as soon as possible after the reaction for potential immune response analysis. No additional sample needed for these planned timepoints; will be taken from PK samples.

6.2.2. Analysis Methods

The incidence of antibodies to daratumumab will be summarized for all subjects who receive at least one dose of daratumumab and have appropriate samples for detection of antibodies to daratumumab. A listing of sample status for antibodies to daratumumab at any time during the study for pharmacokinetic evaluable population will be provided. In addition, subjects who are positive for antibodies to daratumumab will also be listed.

7. BIOMARKER

Biomarker studies are designed to identify markers predictive of response (or resistance) to daratumumab, as well as to gain deeper understanding of NHL. During screening, subjects will be required to provide tumor samples for assessment of CD38 expression based on central testing using investigational IHC methodology under development. In addition to CD38, CD59 expression will be measured by IHC in a designated laboratory as an exploratory biomarker. CD59 is a complement inhibitory protein and can contribute to resistance to CDC, which may be important for daratumumab response.

CD38 and CD59 expression will be summarized for all screened subjects.

A listing of subject CD38 and CD59 expression levels correlated with clinical parameters will be provided for all treated subjects.

REFERENCES

